### 2.2 Study Endpoints

- **Primary endpoint:** Feasibility of obtaining baseline, 30-day, and 6-month clinical and PRO data capture from 200 consented patients.
- **Secondary endpoints:**
  - Percent of patients who enroll on the study platform who had previously received a SARS-CoV-2 booster.

- Percent of patients who enroll on the study platform who went on to receive a SARS-CoV-2 booster after enrollment.
- Percent of patients providing patient reported outcomes (PROs) at each timepoint.
- Among patients providing PROs, percentage for which PROs were viewed by site personnel.
- Percent of patients reporting COVID-19 infection confirmed by home-based or other testing.
- Patient-reported adverse outcomes related to confirmed COVID-19 infection (*as applicable*).
- Hospitalization or death related to COVID-19 as ascertained by full EHR data transmission provided by permission from the patient (*as applicable*).

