#### 4.3 Patient-Generated Health Data

Subjects will be asked to complete questions specific to their health as outlined below. All questions will be administered electronically through the study application. These measures will be obtained to establish health status and COVID-19 infection(s) acquired after study entry. These measures will be included at baseline and at specified timepoints, as outlined in the [Schedule of Activities](#).

The following patient-generated health data (PGHD) will be collected directly from the participating patient and are specified in [Appendix A](#):

- Study eligibility questions
- Contact information and socio-demographics
- Multiple myeloma diagnosis and disease status
- SARS-CoV-2 vaccination history
- Documented COVID-19 infections and treatments
- COVID-19 specific questions

Participants may request additional information about COVID-19 booster vaccinations. Sponsor will receive notification that a participant has requested additional information. Sponsor will also monitor participant requests.

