## **5 Statistical Considerations**

The accrual goal for this study is the enrollment of 200 participants, defined as eligible subjects who access the portal and consent to participate. The primary end point of this study is the proportion of consented participants who provide responses for the PRO instruments; we will separately track the proportion of consented participants who permission access to clinical data through the EHR. We will estimate the proportions and present them descriptively, with a point estimate and an exact binomial confidence interval at each of the PRO time points (Baseline, Day 30, and Day 180). We will also present descriptively the proportion of consented participants who permission EHR access.

We will also report descriptive statistics for each of the secondary objectives, including the proportion of participants who had received a SARS-CoV-2 booster prior to enrollment; the proportion who received a SARS-CoV-2 booster after enrollment; the incidence of patient-reported COVID-19 infection confirmed

by home-based or other testing (per patient report); and the incidence of patient-reported adverse outcomes related to confirmed COVID-19 infection, including long COVID.

Lastly, we will report descriptive statistics on the incidence of hospitalization (at the primary institution at which the patient received myeloma care) or death related to COVID-19 during the 6-month period of observation. We will report estimates for these metrics from two forms of ascertainment: patient-permissioned EHR data transmission and site-provided EHR data abstraction (received under the Data Hub's overarching umbrella protocol). We may perform exploratory analyses of clinical and laboratory correlates of severe adverse COVID-19 related outcomes, sample size permitting, based on site-provided EHR data abstraction (under the Data Hub's umbrella protocol).

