#### After Informed Consent

Participant Information			
Socio-Demographics			
Birth sex	O Male O Female O Other O Decline to Answer		
What race(s) do you identify as? (Select all that apply)	 American Indian or Alaskan Native  Asian  Black or African American  White  Native Hawaiian or Other Pacific Islander  Other  Decline to Answer		
Hispanic ethnicity	O Hispanic or Latino/Latina O Not Hispanic or Latino/Latina O Decline to Answer		
COVID-19 History			
List all COVID-19 vaccinations received.			
Have you received a COVID-19 Vaccination?	O Yes O No O I Don't Know		
Vaccination date	Which vaccine dose(s) did you receive?		Which vaccine did you receive?
/ (MM/YYYY) O I Don't Know	O First Dose O Second Dose O Booster(s) O I Don't Know		O Pfizer O Moderna O Johnson & Johnson O Novavax O I Don't Know
/ (MM/YYYY) O I Don't Know	O First Dose O Second Dose O Booster(s) O I Don't Know		O Pfizer O Moderna O Johnson & Johnson O Novavax O I Don't Know
/ (MM/YYYY) O I Don't Know	O First Dose O Second Dose O Booster(s) O I Don't Know		O Pfizer O Moderna O Johnson & Johnson O Novavax O I Don't Know
/ (MM/YYYY) O I Don't Know	O First Dose O Second Dose O Booster(s) O I Don't Know		O Pfizer O Moderna O Johnson & Johnson O Novavax O I Don't Know
/ (MM/YYYY) O I Don't Know	O First Dose O Second Dose O Booster(s) O I Don't Know		O Pfizer O Moderna O Johnson & Johnson O Novavax O I Don't Know
If you have not received any COVID-19 booster vaccinations, would you be willing to be contacted to discuss the benefits and risks of obtaining one?			O Yes O No O I Don't Know
Would you be willing to receive a yearly COVID-19 vaccination if recommended by your physician?			O Yes O No O I Don't Know
COVID-19 Infections			
List all current and prior COVID-19 infections.			
Have you been diagnosed with COVID-19?	O Yes O No O I Don't Know		
When was your COVID-19 Infection Confirmed?	/ (MM/YYYY) O I Don't Know	How was your COVID-19 Infection Confirmed?	O Home Test Kit O Diagnosis by a Healthcare Professional O I Don't Know
Did This COVID-19 Infection Cause You to be Hospitalized?	O Yes O No O I Don't Know	If Yes, About How Many Days Were You in the Hospital?	- O I Don't Know

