Would you be willing to receive a yearly COVID-19 vaccination if recommended by your physician?		 Yes  No  I Don't Know	
COVID-19 Infections			
List all COVID-19 infections since you completed the Baseline questionnaire.			
Have you been diagnosed with COVID-19 since your last visit?		 Yes  No  I Don't Know	
When was your COVID-19 Infection Confirmed?	/ (MM/YYYY)  I Don't Know	How was your COVID-19 Infection Confirmed?	 Home Test Kit  Diagnosis by a Healthcare Professional  I Don't Know
Did This COVID-19 Infection Cause You to be Hospitalized?	 Yes  No  I Don't Know	If Yes, About How Many Days Were You in the Hospital?	_____  I Don't Know

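### The infection endpoint counts home-test positives, but the only yes/no infection question asks about being 'diagnosed', so some home positives may go unreported

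*Combined protocol and SAP*

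**What the plan says.** Section 2.2 lists the secondary endpoint as "Percent of patients reporting COVID-19 infection confirmed by home-based or other testing". Section 5 reports it descriptively as "the incidence of patient-reported COVID-19 infection confirmed" by home or other testing, on the patient's own report. Section 4.3 makes the questionnaire the source: "These measures will be obtained to establish health status and COVID-19 infection(s) acquired after study entry".

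The questionnaire is in Appendix A. At baseline the infection block asks "Have you been diagnosed with COVID-19". At Time 1 and Time 2 it asks "Have you been diagnosed with COVID-19 since your last visit". Both offer Yes, No and I Don't Know. Above the follow-up question stands the instruction "List all COVID-19 infections since you completed the Baseline questionnaire", and baseline has a similar instruction covering current and past infections. The next items ask when the infection was confirmed, how, and whether it led to hospitalization. The answers on how it was confirmed are a home test kit, "Diagnosis by a Healthcare Professional", and I Don't Know.

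The appendix does not define 'diagnosed', states no branching rule, and has no item asking whether the participant has tested positive.

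**The concern.** The endpoint is about a positive test, including one taken at home. The question that should bring those cases in is about being diagnosed. In the infection block the noun diagnosis belongs only to the healthcare-professional answer, which is offered as the alternative to the home kit. The eligibility survey in the same appendix also uses 'diagnosed' for multiple myeloma, again a clinician's act. A participant who tested positive at home and told no clinician could therefore answer No in good faith.

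The form is completed electronically through the study application, and no interviewer who could clarify the wording is described. The EHR categories in Section 4.2 come from the clinical record and would not be expected to hold a home result that no clinician was told about. At stake are the infection percentage and, through it, the patient-reported adverse outcomes of confirmed infection that Sections 2.2 and 5 also list.

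**Working it through.** **Wording check.** The plan gives no expected incidence, precision target or power figure, so there is no planned number to reproduce. The main check sets the endpoint against the form.

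| Element | Where | Covers a home-only positive? |
|---|---|---|
| Endpoint definition | Sections 2.2 and 5 | Yes, explicitly |
| Block instruction | Appendix A, infection block | Yes by intent (all infections); tests not mentioned |
| Yes/no question | Appendix A, infection block | Unclear ('diagnosed') |
| Confirmation item | Appendix A, infection block | Yes (home kit), but it comes after the yes/no question |

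The form means to include home positives, but the one question that opens the block does not say so.

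**What happens after a No.** There are three cases, and the documents do not say which applies:

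- The follow-on items are hidden: the infection is missed.
- They are shown and left blank: the infection is missed. This is a natural response, because they presuppose an infection.
- They are shown and filled in: the record contradicts itself, and no rule says how to count it.

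**Illustration of size.** The only input from the documents is N = 200 (Section 5: "The accrual goal for this study is the enrollment of 200 participants"). The rest are assumptions:

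- p = true six-month proportion with test-confirmed infection: 10%, 15%, 20%
- h = share of those known only by home test: 40% to 80%
- m = share of the home-only group lost, that is, answering No with nothing recorded in the follow-on items: 10% to 50%

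All 200 are taken to answer. Observed proportion = p × (1 − h × m), so relative loss = h × m:

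- Low: 0.40 × 0.10 = 4%
- Middle: 0.60 × 0.25 = 15%
- High: 0.80 × 0.50 = 40%

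Observed counts are rounded to whole patients. Intervals are exact binomial at an assumed 95% level.

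| True | Low loss | Middle loss | High loss |
|---|---|---|---|
| 20/200 = 10.0% (6.2–15.0) | 19 = 9.5% (5.8–14.4) | 17 = 8.5% (5.0–13.3) | 12 = 6.0% (3.1–10.2) |
| 30/200 = 15.0% (10.4–20.7) | 29 = 14.5% (9.9–20.2) | 26 = 13.0% (8.7–18.5) | 18 = 9.0% (5.4–13.9) |
| 40/200 = 20.0% (14.7–26.2) | 38 = 19.0% (13.8–25.1) | 34 = 17.0% (12.1–22.9) | 24 = 12.0% (7.8–17.3) |

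The grid of p (three values), h (40%, 60%, 80%) and m (10%, 25%, 50%) has 27 combinations. The interval around the observed value excludes the true value in three of them, all with m = 50%.

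**The case against.** The strongest reply is that the form, read as a whole, is clear. The block is about infections, its instruction asks for all of them, and the home kit is the first confirmation answer. If the follow-on items appear only after a Yes, that answer makes sense only when a home positive counts as 'diagnosed'. This stands as evidence of intent and probably reduces the error. It does not remove it, because the instruction does not mention tests and the home-kit answer comes after the ambiguous question.

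Three stronger readings are tempting, and the documents do not support them.

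- *Home positives are irrecoverably lost.* That needs a branching rule, and none is documented. If all items are displayed, a date and a home-kit answer could still be recorded after a No.
- *The reported infection percentage is biased down overall.* Only the home-test misreading has a known direction. The block also admits clinician diagnosis with no stated test, and allows I Don't Know for the method of confirmation. Counting those would push the percentage up, so the net direction is unknown.
- *The hospitalized share of infections is biased up.* The form does ask about hospitalization for each infection, and the Study Summary objective names patient report as well as EHR capture. But the plan specifies no such share: Sections 2.2 and 5 take COVID-19 hospitalization or death from EHR sources.

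It is also fair to say that under many of the assumed inputs the loss is smaller than the sampling error at N = 200, and that the endpoint is secondary and descriptive. Both points limit the importance of the problem. Neither is a reason to keep a question that does not match its endpoint when rewording it costs so little.

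**Conclusion.** The point holds as a wording mismatch with a plausible undercount in a named secondary endpoint. It is not a failure to collect home-test results. A home-only positive can reasonably be answered No, and if nothing is then recorded in the follow-on items the infection is missed. This error taken alone can only lower the reported percentage.

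Its size cannot be known from the documents, which give no incidence, home-test share or misreading rate. The relative loss of 4% to 40% rests wholly on the assumed ranges for h and m, and the upper end needs half of all home-only positives to be lost. The primary endpoint, which is the proportion giving PRO responses, is not affected. The change is worth making because it is cheap, not because a large bias has been shown.

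**What to change.** In the infection block of Appendix A:

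1. At baseline, Time 1 and Time 2, reword the yes/no question to: *Have you had a positive COVID-19 test (home test kit or any other test), or been told by a healthcare professional that you had COVID-19?*
2. At Time 1 and Time 2, attach one look-back period to it that agrees with the block instruction. The instruction now runs from baseline, while the question runs from the last visit. At Time 2, for someone who completed Time 1 on schedule, these differ by the first 30 days (180 days against 180 − 30 = 150).
3. Add a laboratory, pharmacy or clinic test answer to the confirmation item. The reworded question still admits clinician diagnosis without a test, and the present answers cannot separate that from other testing. With the added answer, test-confirmed infections (the endpoint) can be counted apart from clinician diagnosis alone.
4. State whether the follow-on items are shown after a No and, if so, how a completed item after a No is counted.

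The cost is a small edit to three electronic forms with IRB notification. The number of questions does not change, and one answer choice is added. Any answers already given to the present wording should be tabulated separately from those given to the new one.

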### **Time 1**

Time 1 will occur 30 days (+ 15 days) following baseline and the following will be completed virtually:

- EHR data transmission
- PGHD
- PROs

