### **Time 2**

Time 2 will occur 180 days (+ 30 days) following baseline and the following will be completed virtually:

- EHR data transmission
- PGHD
- PROs

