## Time 1 (30 Days) and Time 2 (180 Days)

COVID-19 History			
List all COVID-19 vaccinations received since you completed the Baseline questionnaire.			
Have you received a COVID-19 vaccine since your last visit?		 Yes  No  I Don't Know	
Vaccination Date	Which Vaccine Dose Did You Receive?	Which Vaccine Did You Receive?	
/ (MM/YYYY)  I Don't Know	 First Dose  Second Dose  Booster(s)  I Don't Know	 Pfizer  Moderna  Johnson & Johnson  Novavax  I Don't Know	
/ (MM/YYYY)  I Don't Know	 First Dose  Second Dose  Booster(s)  I Don't Know	 Pfizer  Moderna  Johnson & Johnson  Novavax  I Don't Know	
/ (MM/YYYY)  I Don't Know	 First Dose  Second Dose  Booster(s)  I Don't Know	 Pfizer  Moderna  Johnson & Johnson  Novavax  I Don't Know	
/ (MM/YYYY)  I Don't Know	 First Dose  Second Dose  Booster(s)  I Don't Know	 Pfizer  Moderna  Johnson & Johnson  Novavax  I Don't Know	
/ (MM/YYYY)  I Don't Know	 First Dose  Second Dose  Booster(s)  I Don't Know	 Pfizer  Moderna  Johnson & Johnson  Novavax  I Don't Know	
If you have not received any COVID-19 booster vaccinations, would you be willing to be contacted to discuss the benefits and risks of obtaining one?		 Yes  No  I Don't Know	

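### The shared follow-up form gives two recall periods for the same COVID-19 items, so infections and boosters after enrolment may be under-reported and an infection event count could be inflated

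*Combined protocol and SAP*

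**What the plan says.** Appendix A has one questionnaire for both follow-up time points. Each of its two blocks has a header telling the participant what to list, followed by a yes/no item.

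- Vaccination: the header reads "List all COVID-19 vaccinations received since you completed the Baseline questionnaire"; the yes/no item reads "Have you received a COVID-19 vaccine since your last visit".
- Infection: the header reads "List all COVID-19 infections since you completed the Baseline questionnaire"; the yes/no item reads "Have you been diagnosed with COVID-19 since your last visit".

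Event dates are recorded as month and year, with an option for not knowing. The Baseline form separately asks for earlier events, for example "List all current and prior COVID-19 infections".

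On timing, Section 4.5 states "Time 1 will occur 30 days (+ 15 days) following baseline" and "Time 2 will occur 180 days (+ 30 days) following baseline and the following will be completed virtually". Neither Appendix A nor Section 4.5 defines a visit. Section 9.2, on payments, does call Time 0, Time 1 and Time 2 study visits.

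Section 2.2 expresses the two affected secondary endpoints as percentages of patients: those reporting a confirmed infection, and those receiving a booster after enrolment. Section 5 keeps a proportion for boosters but speaks of the incidence of infection without saying whether patients or events are counted. It gives no rule for combining Time 1 and Time 2 reports.

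**The concern.** At Time 2 the header and the yes/no item need not refer to the same period, and nothing says which governs. Two participants with the same history could answer differently and both be following the form.

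The word 'visit' adds a second ambiguity. Everything is completed remotely, and Section 3.2 requires participants to be on active myeloma treatment, so many will have a recent clinic appointment. Someone who takes the question to mean that appointment would answer for a shorter period than intended.

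There is limited backup if the form misses an event. Section 4.3 gives these items the job of establishing infections acquired after study entry, and Section 5 takes infection from patient report. The record categories in Section 4.2 do not name vaccination, and a positive home test need not reach a medical record. What is at stake is under-reporting in two secondary endpoints and, depending on the unit of analysis, some double counting of infections.

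**Working it through.** The documents state no figure that depends on this wording. The 200 is an accrual goal, so there is no calculation to reproduce. The check compares the two recall periods under each reading of 'visit'.

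**Inputs (Section 4.5).** Time 1 falls on Day 30 to 45 and Time 2 on Day 180 to 210.

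**Reading A: 'visit' means study visit.**

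- At Time 1 the last visit is Baseline, so the periods coincide.
- At Time 2 they differ over Baseline to Time 1. As a share of follow-up this is T1/T2: 30/180 = 16.7% at the nominal days; 30/210 = 14.3% at the least; 45/180 = 25.0% at the most.
- A participant who completes both forms is covered: Time 1 asks about Baseline to Time 1, and Time 2 asks at least about what follows.
- A participant who skipped Time 1 has Baseline as the last visit, so the periods coincide again at Time 2.

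**Reading B: 'visit' means clinic appointment.** Each form then reaches back only to the last appointment. With an interval of w days, the two nominal forms together cover (min(w, 30) + min(w, 150))/180 of follow-up, which is below 1 whenever w is under 150. The loss depends on w and on the share of participants who read the item this way. The documents give neither, so no estimate follows.

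**Relisting at Time 2.** A participant who follows the header will list early events a second time.

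- Percentage of patients: someone reported twice is still one patient, so nothing changes.
- Count of events: under constant risk a fraction T1/T2 of events precedes Time 1. If all of these are repeated, the count rises by 14.3% to 25.0%.
- For scale, assume 10% infected with one event each, or 20 of 200: 20 × 0.143 = 2.9 and 20 × 0.25 = 5.0, so about 3 to 5 extra records. The 10% is illustrative. The exact 95% interval for 20/200 is 6.2% to 15.0%.

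**Can month-only dates identify repeats?** Taking enrolment evenly over 730 days and events evenly over follow-up, 52% of events before Time 1 fall in the same calendar month as Time 1 when it is on Day 30, and 35% when it is on Day 45. For those, month and year alone cannot tell a repeated report from a new event.

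**The case against.** The strongest reply is that 'visit' has a natural meaning here. Section 9.2 uses the term for the three time points, and on that reading both completers and Time 1 skippers are covered. The Baseline header also sits directly above each yes/no item, which makes the clinic reading less likely. Appendix A is a flat list of data elements, so it does not show whether a 'No' closes the list or whether the application pre-fills earlier entries. This removes any claim of certain loss. It does not settle how patients will read the word, because they see the questionnaire and not the payment section.

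A reader might infer several stronger things that the documents do not support.

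- *Events will be missed or double-counted.* Loss requires the clinic reading or some other departure from the study reading, and relisting cannot alter the Section 2.2 percentages.
- *Time 1 non-responders lose 17% of their risk period.* Under the study reading, their last visit is Baseline.
- *About 13% to 21% of events are lost.* That range comes from assuming that 25% of participants misread the item and that appointments are 14 to 56 days apart. Neither figure is in the documents.
- *Reports up to Day 210 breach a six-month limit.* Section 5 attaches the 6-month period to hospitalization or death; it states no Day 180 cut-off for patient-reported infections or boosters.
- *Month-only dates hide whether an event followed enrolment.* The Baseline lists and the follow-up headers already separate the two periods.
- *The problem is beyond repair at analysis.* Counting each patient once removes duplicates without exact dates. Only an event that was never reported is beyond recovery.

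**Conclusion.** The inconsistency is real and appears in both blocks of the form. With 'visit' read as study visit, it is confined to Time 2 and to 14% to 25% of follow-up (17% at the nominal days), with no loss for a participant who completes both forms. With 'visit' read as clinic appointment, infections and boosters may be under-reported at either time point, to an extent that cannot be derived from the documents.

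The inflation of about 14% to 25% applies only if Section 5 counts infection events rather than patients. It also assumes constant risk and that every event before Time 1 is listed again, so it is an upper case.

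Severity is minor to moderate. The affected endpoints are secondary and descriptive, and the primary endpoint, PRO completion, is untouched. The point is still worth acting on, because an answer given to an ambiguous question cannot be reinterpreted afterwards.

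**What to change.** 1. In the two yes/no items of the follow-up form, replace the reference to the last visit with the Baseline anchor already used in the list headers, and auto-fill the date on which that participant completed the Baseline questionnaire. The headers need no change.
2. At Time 2, display the entries already reported at Time 1. A Baseline anchor invites participants to repeat them, so this step belongs with the first.
3. In Section 5, state that a participant counts once for infection, and once for booster, if the event is reported at Time 1 or Time 2. This also settles the unit for infection incidence.
4. Optionally, add a day field that may be left unknown, to help match repeat reports. This is a preference and not the correction of an error.

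The cost is a wording change in the electronic form and an IRB amendment, with slight extra burden on participants if the day field is added. The sample size of 200 does not change.
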